## Research Question and Aims

**Specific Aim #1: Quantify 4DCT wrist biomarkers during resisted and unresisted tasks in healthy controls.** Healthy controls without any history of wrist injury or diseases will be scanned using 4DCT during wrist movement to characterize gapping at the scapholunate, radiolunate, and radioscapheoid joints (“radiocarpal joint and scapholunate interval”) as well as at the scaphotrapezium, scaphotrapezoid, and trapezotrapezoid joints (“scaphotrapeziotrapezoid [STT] joint”), as well as any other wrist joints captured within the imaging fields-of-view (i.e., trapeziometacarpal [TMC] joint). The existing device used to hold and guide subject’s wrists will be modified to provide resistance to movements. The scientific premise for this aim is our pilot cadaveric and patient imaging using 4DCT.

**Hypothesis:** *Scapholunate distances and bilateral asymmetry will be greater in the resisted tasks as compared to the unresisted tasks in both male and female subjects. Secondarily, gapping in females will be greater than males.*

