### **Aim 1:**

Bilateral 4DCT scans will be performed on 30 healthy controls (15 males, 15 females) without any history of wrist injury or disease. Subjects will be randomly assigned to one of three groups of 10 subjects using stratified randomization to ensure equal distribution of sex in each group (5 males, 5 females); order of testing (unresisted and resisted) will be randomized within each group. 4DCT wrist data will be obtained while subjects in each group perform one of the following tasks through a full range of motion, bilaterally: 1) passive and active grip; 2) unresisted and resisted flexion-extension; and 3) unresisted and resisted radial-ulnar deviation. Subjects in group 1 will perform the task with the wrist in neutral position. Auditory cues will be given to subjects in all groups via metronome to ensure the full motion cycle is performed in 2 seconds (length of each individual scan). Resistance will be standardized across participants. The dynamic image sequence will be processed using existing software tools to obtain metrics quantifying the size and location of gapping (palmar or dorsal) at the scapholunate, radiolunate, and radioscaphoid joints as well as at the scaphotrapezium, scaphotrapezoid, and trapezotrapezoid joints—as well as any other wrist joints that may be captured in the imaging field-of-view—during the movement cycles.

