## Data Analysis

## Data Analysis Plan:

### **Aim 1:**

Normalized volar/dorsal location of the gapping at the scapholunate, radioscapoid, and radiolunate joints as well as the scaphotrapezium, scaphotrapezoid, and trapezotrapezoid joints—as well as other wrist joints in the acquired field-of-view—for the 15 male and 15 female subjects will be analyzed. Three-dimensional bone shape variations will be quantified. Magnitude and direction of contact center migration, bilaterally, will be analyzed during the 17 time steps during each movement. The primary assessment will be of the scapholunate distances as well as STT interosseous distances and bilateral asymmetry between the unresisted and resisted tasks in both male and female subjects. The secondary assessment will be of the scapholunate gapping as well as STT interosseous distance differences between males and females. The differences in bilateral migration of the contact center in the one limb as a percent normalization relative to the contralateral limb values will be determined and described using the t-distribution. These analyses will be repeated by sex, and other subgroups that become apparent during the study. With a sample size of 30, using a two-sided size 0.05 t-test, we will have 80% power to detect an effect size of 0.53 for the analysis of quantitative outcomes.

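### The one power statement (80% at effect size 0.53) names no contrast: it reproduces only for a paired test pooling all 30 subjects, while the planned male-versus-female comparison has 28.9% power at 0.53

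*Combined protocol and SAP*

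**What the plan says.** The Data Analysis Plan, Aim 1, ends with the only power statement in the document. For 30 subjects and a t-test at the two-sided 0.05 level, it claims that "we will have 80% power to detect an effect size of 0.53 for the analysis of quantitative outcomes". The type of t-test and the SD behind 0.53 are not given.

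The same paragraph sets out several analyses:

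- The primary assessment compares unresisted with resisted tasks, in males and in females.
- The secondary one is between subjects: "The secondary assessment will be of the scapholunate gapping as well as STT interosseous distance differences between males and females".
- The limb-to-limb differences in contact-centre migration, "relative to the contralateral limb values will be determined and described using the t-distribution".
- Finally, "These analyses will be repeated by sex, and other subgroups that become apparent during the study".

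The sex comparison is also a stated hypothesis in Research Question and Aims: "Secondarily, gapping in females will be greater than males".

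On design, Study Design and Methods, Aim 1, gives 15 males and 15 females and says "Subjects will be randomly assigned to one of three groups of 10 subjects", with five of each sex per group. Each group performs one of three tasks, in both the unresisted (or passive) and the resisted (or active) condition. The analysis plan does not say whether the three tasks are combined.

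**The concern.** The sentence closes a paragraph that contains both within-subject and between-subject comparisons, and it is limited to neither. Scapholunate gapping and STT distance are quantitative outcomes, and the sex comparison uses the same 30 people, so a reader may fairly take the 80% to apply to it. That reader would expect a 20% chance of missing a true sex difference of 0.53 SD. The actual chance is about 71% (100% − 28.9%). A non-significant sex result could then be given more weight than it can bear, on a hypothesis that the protocol states.

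The figure is also conditional for the primary contrast. A sample of 30 is available for resisted versus unresisted only if grip, flexion-extension and radial-ulnar deviation are analysed together.

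**Working it through.** **Inputs.** From the Data Analysis Plan, Aim 1: N = 30, two-sided alpha 0.05, t-test, effect size 0.53, power 80%. From Study Design and Methods, Aim 1: 15 males and 15 females; three task groups of 10. Target accrual is 31, but one of these replaces a subject who lost half the dataset, so 30 is used.

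**Assumptions.** Each outcome is tested singly, with one summary value per subject. The plan has two wrists and 17 time steps and gives no rule for summarising them.

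**Formula.** Power = P(|T| > t(0.975, df)), where T is noncentral t with noncentrality δ.

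- Paired or one-sample: δ = d × √n, df = n − 1.
- Two-sample: δ = d × √(n₁n₂/(n₁+n₂)), df = n₁ + n₂ − 2.

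**Step 1: the plan's own figure.** Paired, n = 30: δ = 0.53 × √30 = 2.903, df = 29, critical value 2.045. Power is **80.1%**, and the effect detectable at 80% is 0.529. The stated figure reproduces. With task in the model (df = 27), the values are 79.9% and 0.531.

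**Step 2: can a two-sample test give the figure?** No. 15 vs 15 gives 28.9%, and even 30 per group would give only 52.3%. This is why the paired or one-sample reading is inferred.

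**Step 3: males versus females.** n₁n₂/(n₁+n₂) = 225/30 = 7.5; δ = 0.53 × √7.5 = 1.451, df = 28, critical value 2.048. Power is **28.9%**, and the detectable effect is **1.06** between-subject SD. With task in the model (df = 26), the values are 28.7% and 1.06. A one-sided 0.05 test, which the plan does not specify, would give 41.0%.

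**Step 4: smaller paired samples.**

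| Contrast | n | Power at 0.53 | Detectable effect at 80% |
|---|---|---|---|
| Paired, all tasks pooled | 30 | 80.1% | 0.53 SD of the paired difference |
| Paired, within one sex | 15 | 48.1% | 0.78 SD of the paired difference |
| Paired, within one task | 10 | 32.3% | 1.00 SD of the paired difference |
| Males vs females | 15 vs 15 | 28.9% | 1.06 SD of the per-subject value |

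The first three rows and the last are in different units, so 0.53 and 1.06 cannot be compared in millimetres.

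**Step 5: sensitivity to assumptions the documents do not settle.**

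- *Two wrists.* Suppose the wrists are averaged and the effect is scaled on the per-wrist SD, so that the SD shrinks by √((1+ρ)/2). For an assumed between-wrist correlation ρ of 1, 0.5 and 0, power for the sex comparison is 28.9%, 36.7% and 50.9%.
- *Pooling without task in the model.* Suppose task means lie at −s, 0 and +s, with s = 0.25, 0.5 or 1 within-task SD (assumed). By simulation, power for the within-subject contrast falls to 78.8%, 75.2% and 60.1%, and for the sex comparison to 27.5%, 23.4% and 12.7%. With task in the model, both stay at about 80% and 29%.

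**The case against.** The strongest reply is that the sentence was meant for the primary contrast alone. It gives one sample size, one test and one effect size, and only a paired or one-sample formula yields 0.53. The reference to quantitative outcomes may simply separate continuous from categorical measures. Powering only the primary contrast is ordinary practice, and the sex comparison is labelled secondary. This has force: that the 80% covers the sex comparison is a matter of reading, not an explicit claim. But the text sets no such limit, and under the narrow reading a hypothesised comparison has no precision figure at all. One rewording settles both.

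Stronger readings are tempting and should be resisted:

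- A reader might infer that the 80% is miscalculated. It is not; it reproduces.
- A reader might infer that the trial needs more subjects because the sex comparison is weak. The documents do not undertake to power that comparison separately.
- A reader might infer that the primary figure is secure once the sex comparison is set aside. It holds only if tasks are pooled, which the plan does not state. The primary assessment is also worded for both sexes, which could mean within each sex.
- A reader might argue that a 15 vs 15 confidence interval could never lie within ±0.53 SD. That is true only in units of the observed SD, and the plan draws no equivalence conclusion that would depend on it.
- A reader might extend the 80% to limb versus contralateral limb. The plan speaks there of description by the t-distribution and specifies no test.

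**Conclusion.** The concern holds as a fault of scope, not of arithmetic. The power statement is correct for one unstated case: a paired or one-sample test pooling all 30 subjects across tasks (80.1%). Read as written, it also reaches the male-versus-female assessment, where power at 0.53 is 28.9% and the detectable effect is 1.06 SD. It is silent on whether the primary contrast has 30 subjects or 10 per task.

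The power figures follow directly from the stated design, given one summary value per subject and single tests. Averaging wrists raises the sex comparison to at most 50.9% over the correlations considered (0 to 1), so its shortfall from 80% does not depend on that choice. Less certain is whether the sponsor meant the sentence to cover the sex comparison. The statement should be corrected, but this does not invalidate the study.

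**What to change.** Replace the power sentence with text along these lines:

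> For each quantitative outcome, tested singly at two-sided 0.05 with one summary value per subject, 30 subjects pooled across the three tasks, with task in the model, give 80% power for a within-subject resisted-versus-unresisted difference of 0.53 SD of the within-task paired difference. If tasks are analysed separately (n=10) the detectable effect is 1.00 SD, and within one sex (n=15) it is 0.78 SD, of the paired difference. For males versus females (15 vs 15) the detectable effect is 1.06 SD of the per-subject value (power at 0.53 is 29%), and this comparison will be reported as an estimate with a 95% confidence interval.

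The sponsor should state whether tasks are pooled and keep only the figures that match. The 80% should not be attached to the limb-to-limb comparison unless a test is specified for it.

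The cost is a few sentences and one analysis decision (pooling, with task in the model), recorded before analysis. Enrolment is unchanged. The drawback is that the stated figures look less favourable.
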